5. STATISTICAL ANALYSES

5.1. Disposition

The total number of participants who were screened (who have signed the informed consent), reasons for screen failure and the number in each study population will be summarized based on the Screened Analysis Set.

The end of treatment status (ongoing/discontinued) together with the primary reason for discontinuing the treatment will be summarized as follows:

- Death
- Disease Progression
- Removal From Study (Investigator/Sponsor Decision)
 - Adverse Event
 - Excluded Concomitant Medication or Procedure
 - Compliance (Study Treatment/Study Assessments)
 - New Information/Findings
 - Study/Site is Cancelled
 - Relocation
 - Lost to Follow-Up
 - Other
- Withdrawal of Consent
- Study Completion
- Other

In addition, the end of study status will be summarized including if a participant is participating in the long-term follow-up.

All treatment and study discontinuation data will be listed. A by-participant data listing of inclusion and exclusion criteria not met will be presented.

5.2. Demographics, Baseline Characteristics, and Medical History

Demographics and baseline characteristics will be summarized for the Full Analysis Set. In addition, medical history (including any history of infertility), disease characteristics, prior systemic treatment, radiation and surgery will also be summarized for the Full Analysis Set. Demographic and baseline data, disease characteristics, and prior systemic treatment for each participant will be provided in data listings. In addition, data listings containing the details for prior surgery coded with MedDRA (version 27.0) and prior radiation will be provided.

5.2.1. Demographics

Demographics will include univariate statistics for age at time of informed consent (years), baseline weight, baseline height, baseline body mass index (BMI) (kg/m^2), baseline FOSI, and categorical summaries for age groups, women of childbearing potential (yes / no), baseline ECOG, race, and ethnicity.

5.2.2. OvGCT History and baseline Characteristics

Baseline disease characteristics to be summarized including time (in months) since date of original OvGCT diagnosis to first study treatment, age at the original disease diagnosis, refractory disease (yes/no), time from refractory (months), relapse (yes/no), time from the original relapsed OvGCT diagnosis and the most recent relapse to first study treatment (months), history of prior surgery for OvGCT (yes/no), time (months) since the most recent surgery to first study treatment, prior radiation (yes/no), time (months) since the most recent radiotherapy to first study treatment, prior systemic treatment (yes/no), time (months) since the most recent prior treatment (surgery, radiotherapy and systemic treatment) to first study treatment, number of target lesions, number of non-target lesions, and baseline tumor size, defined as the sum of the target lesion diameters per RECIST v1.1.

5.2.3. Medical History

The following medical history will be summarized:

- time in months since last menstrual cycle to first study treatment,

- number and percentage of participants with any history of amenorrhea, menstrual irregularities, or infertility, and
- any clinically significant past or ongoing medical conditions, by MedDRA (version 27.0) System Organ Class (SOC) and Preferred Term (PT).

5.2.4. Prior Systemic Therapies for OvGCT

Prior systemic therapies for OvGCT will be coded with WHO Drug March 2022 version or higher and will be summarized by anatomic therapeutic class (ATC) and PT.

Details about each line of treatment, including agents start and stop date, reason for discontinuation, best overall response will be listed. The number of lines of systemic treatment, prior use of Bevacizumab (yes/no), time (months) since most recent Bevacizumab use and time (months) since most recent systemic treatment line to first study treatment will be summarized along with other disease characteristics.

5.3. Primary Efficacy Endpoint

All efficacy endpoints will be analyzed using the Full Analysis Set. The primary efficacy endpoint is objective response rate, defined as the proportion of participants with CR + PR.

Tumor response and progression of cancer under study in real time will be evaluated locally at each study site according to RECIST v1.1.

To be assigned a status of PR or CR, changes in tumor measurements must be confirmed by repeat assessments that will be performed no less than 4 weeks after the criteria for response are first met. In order for a valid value of Stable Disease (SD) to be assigned, there must be evidence of stable disease for at least 7 weeks (the 8-week scan interval inclusive of a 1-week window per the SoA) from start of treatment. If the minimum time for SD has not been met on the first assessment, the assignment of BOR will depend on subsequent response assessments.

Participants who do not have follow up data after a first assessment of SD prior to the minimum time requirement will be considered as not evaluable (NE).

The best overall response is determined by the following hierarchy: CR > PR > SD > PD > NE. Participants with a best overall response as confirmed CR or PR during the study will be

responders. Participants who had no post-baseline tumor assessment and those whose best overall response is no evaluable or less than CR or PR will be analyzed as non-responders.

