  - b. Chest imaging: CXR or CT (contrast not required) required as described in the SoA and should be obtained per institutional standards.
  - c. EOT Visit: Scans only required if not performed within the last 6 weeks.
- 18. **Pre-Enrollment Review Form:** This form should be submitted at least 2 days prior to C1D1 in order to allow the Medical Monitor to review and approve eligibility prior to the participant being enrolled in the Interactive Response Technology IRT system (refer to the study reference manual for additional details)
- 19. **Enrollment:** Participants will be enrolled during the C1D1 visit, using the IRT system, only after all baseline assessments have been completed and participant has been confirmed to meet all eligibility criteria.
- 20. **Study treatment dispensing:** Participants will be dispensed study treatment using the IRT every cycle for the first year (C1-C13) and then every 3 cycles thereafter.
- 21. **Study treatment administration/Dosing Diary:** The first dose of study treatment (3 × 50 mg tablets) will be administered orally at the site at C1D1 followed by a 1-hour observation period. Following the first dose, participants will self-administer study treatment at 150 mg (3 × 50 mg tablets) twice daily (BID) (approximately every 12 hours, without regard to food) continuously in 28-day cycles throughout the study. Participants should record daily administration of each study treatment dose in the Dosing Diary. Refer to [Section 8](#) for more detail.
- 22. **AEs/AESIs/SAEs:** Will be monitored and documented from the time of informed consent up to 30 days after the last dose of study treatment. Participants reporting AEs/AESIs/SAEs of reproductive system disorders will have hormone levels assessed every 3 months until event resolution (or for at least 90 days after discontinuing study treatment).
- 23. **Every 3 Cycles and On:** Following C13D1 participants will return every 3 cycles for study visits until end of study participation.
- 24. **Remote Monthly Wellness Checks:** Monthly (every 28 days [+/- 2 days]) telephone or email contact is required following C13D1 until EOT. The wellness checks may be replaced by a face-to-face interaction when study visits occur, provided the wellness information can be obtained during the visit. Refer to [Section 11.2.7](#) for more detail.

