## 9. DISCONTINUATION OF STUDY TREATMENT AND PARTICIPANT DISCONTINUATION/WITHDRAWAL

It may be necessary for a participant to permanently discontinue study treatment (nirogacestat) early. In this case, the participant will return to the site for an EOT visit and a post dose safety

follow-up (FUP) visit (refer to SoA; [Section 1.3](#) for a complete list of required assessments to be conducted).

Reasons for discontinuation of study treatment at any time may include:

- Clinical (including physical examination) or radiographic (using RECIST v1.1) evidence of progressive disease (PD);
  - Treatment after Initial Evidence of Disease Progression
    - Study treatment may be continued at the investigator's discretion if the participant is clinically stable as defined by the following criteria:
      - Absence of clinical signs and symptoms of disease progression
      - No decline in ECOG performance status
      - Absence of progressive tumor at critical anatomical sites (e.g., cord compression) requiring urgent alternative medical intervention.
    - The participant will be reassessed at the next protocol-defined CT or MRI scan for tumor measurement in order to rule out pseudo-progression.
      - If repeat imaging demonstrates CR, PR, or SD compared to the first scan that showed disease progression, treatment with study treatment may be continued.
      - If repeat imaging demonstrates PD, defined as  $\geq 10\%$  increase in tumor burden compared to the first scan that showed disease progression, participants should be discontinued from study treatment.
    - All decisions to continue study treatment beyond initial progression must be discussed with the Medical Monitors and documented in source documents.
  - Adverse events requiring removal from protocol therapy as stated in [Section 9.1](#). Any SAE (refer to [Appendix A5-1.3](#) for SAE criteria), clinically significant AE (refer to QTcF stopping criteria, [Section 9.1.2](#)), severe laboratory abnormality (refer to liver chemistry stopping criteria, [Section 9.1.1](#)), any grade  $\geq 3$  hypersensitivity reaction, anaphylaxis, intercurrent illness, or other medical condition which indicates to the Investigator that continued participation is not in the best interest of the participant;
  - The initiation of emergent treatment (e.g., radiotherapy, surgery, or systemic therapy including chemotherapy, small molecule inhibitors, immunotherapy, or targeted therapy) for granulosa cell tumor;

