5.3.2. Sensitivity Analyses of Objective Response Rate

There is no sensitivity analysis of objective response rate. Post hoc analyses may be performed if deemed necessary.

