5.4.4. Duration of Response (DoR)

DoR will be summarized with standard summary statistics and will also be analyzed using the Kaplan-Meier method for confirmed responders only. Quartiles (i.e., the 25th, 50th, and 75th percentile estimates) and the 2-sided 95% confidence intervals will be presented. If progression

or death was not observed, the participant will be censored according to the censoring rule for PFS (see Table 3). If there are censored participants in DoR, time to censoring will be used to summarize the range. The Kaplan-Meier plot will be provided.

By-participant listing will be provided for responders. The listing will include number of completed cycles before first response, date of first response, date of first disease progression or death if any, censored or event will be marked.

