5.5. Exploratory Efficacy Endpoints

5.5.1. Time to Event Endpoints

Exploratory time to event endpoints include PFS, PFS on continued treatment, PFS2 and OS.

For each endpoint, quartiles (i.e., the 25th, 50th, and 75th percentile estimates) and the 2-sided 95% confidence intervals will be calculated from the Kaplan-Meier method. Survival probability and associated 95% CIs will be estimated at 6 months, 1 year, 18 months and 2 years as well. The number of events, number of participants censored, number of participants for each reason of censoring will be provided. The Kaplan-Meier plot of the survival distribution function will be presented with the number of participants at risk over time.

PFS

For PFS, participants who have no documented disease progression and death will be censored according to the rules in Table 3. For PFS-6 and DoR, similar censoring rules should be used if applicable.

Table 3 PFS and DoR censoring rules

Situation	Date of Censoring or Event	Outcome
No adequate tumor assessment at baseline or post-baseline and the participant has not died	Date of first dose of study treatment	Censored
No documented progression or death	Date of last adequate disease status assessment	Censored

Situation	Date of Censoring or Event	Outcome
Progression based on RECIST v1.1 with ≤ 1 missing consecutive scheduled tumor assessment before progression	Date of the earliest assessment that results in a finding of progression	Event
Death without documented progression with ≤ 1 missing consecutive scheduled tumor assessment before death	Date of death	Event
New anticancer therapy or procedure started prior to documented disease progression	Date of last adequate disease status assessment before the new therapy	Censored
Progression/Death after two or more missing scheduled tumor assessments	Date of last adequate disease status assessment before the missed assessments	Censored

Progression-free survival on continued nirogacestat treatment and PFS2

For the PFS analysis on continued nirogacestat treatment, only participants who continued the study treatment after the initial evidence of disease progression will be included. Participants who are alive and have not had a second progression will be censored at the last adequate disease status assessment date.

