Partial Response (PR):	At least a 30% decrease in the sum of the LD of target lesions, taking as reference the baseline sum of LD.
Progressive Disease (PD):	At least a 20% increase in the sum of the LD of target lesions, taking as reference the smallest sum of LD recorded since the treatment started or the appearance of one or more unequivocal new lesions. In addition to the relative increase of 20%, the sum must also demonstrate an absolute increase of at least 5 mm.
Stable Disease (SD):	Neither sufficient shrinkage to qualify for PR nor sufficient increase to qualify for PD, taking as reference the smallest sum LD since the treatment started.

Evaluation of best overall response

The best overall response is the best response recorded from the start of the study treatment until disease progression/recurrence (taking as reference for PD the smallest measurements recorded since the start of study treatment). The participant's best response assignment will depend on the achievement of both measurement and confirmation criteria (defined below).

Time point response: participants with target disease

Target Lesions	Nontarget Lesions	New Lesions	Overall Response
CR	CR	No	CR
CR	Non-CR/non-PD	No	PR
CR	Not evaluated	No	PR
PR	Non-PD or not all evaluated	No	PR
SD	Non-PD or not all evaluated	No	SD
Not all evaluated	Non-PD	No	NE
PD	Any	Yes or No	PD
Any	PD	Yes or No	PD
Any	Any	Yes	PD

CR=Complete Response; NE=Not Evaluable; PD=Progressive Disease; PR=Partial Response; SD=Stable Disease.

Participants with a global deterioration of health status requiring discontinuation of study treatment without objective evidence of disease progression at that time will be classified as having “symptomatic deterioration”. Every effort should be made to document the objective progression even after discontinuation of treatment.

Confirmation

- **Confirmation of response:**
 - The main goal of confirmation of objective response is to avoid overestimating the response rate observed. In cases where confirmation of response is not feasible, it should be made clear when reporting the outcome of such studies that the responses are not confirmed.
 - To be assigned a status of PR or CR, changes in tumor measurements must be confirmed by repeat assessments that will be performed no less than 4 weeks after the criteria for response are first met.

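### The primary ORR is not closed at new anticancer therapy, as PFS and DoR are, so a scan taken afterwards can confirm a response credited to nirogacestat

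*SAP*

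**What the plan says.** **Primary endpoint.** SAP 5.3: "Participants with a best overall response as confirmed CR or PR during the study will be" responders. SAP 3.1 refers to SAP 8.1 for the RECIST details, and there the window is: "The best overall response is the best response recorded from the start of the study treatment until disease progression/recurrence". Protocol Appendix 3 has the same definition. On confirmation, SAP 5.3 says that a CR or PR "must be confirmed by repeat assessments that will be performed no less than 4 weeks after the criteria for response are first met". That sets a minimum interval but no maximum, and no condition on what treatment the participant is receiving at the confirming scan. SAP 5.3.2 adds: "There is no sensitivity analysis of objective response rate".

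**Time-to-event endpoints.** One row of SAP Table 3 reads "New anticancer therapy or procedure started prior to documented disease progression". Its outcome is censoring at the last adequate assessment before that therapy. SAP 5.4.4 carries the rule to DoR: absent progression or death, "the participant will be censored according to the censoring rule for PFS (see Table 3").

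**Conduct.** Protocol 9 lists among the reasons for stopping nirogacestat: "The initiation of emergent treatment (e.g., radiotherapy, surgery, or systemic therapy including chemotherapy, small molecule inhibitors, immunotherapy, or targeted therapy") for the tumor. Stopping leads to an EOT visit within 7 days of the decision. Footnote 17c of the Schedule of Assessments says: "EOT Visit: Scans only required if not performed within the last 6 weeks".

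**The concern.** ORR and DoR describe the same responses but follow participants to different end points. A scan that Table 3 treats as contaminated by another treatment remains admissible for best overall response. If a first PR was seen on nirogacestat and the confirming scan falls after surgery, radiotherapy or another drug, the confirmation may reflect that other treatment, yet the plan as written still counts a confirmed responder.

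The error runs one way. Best overall response takes the best category reached, so an extra scan after new therapy can add a responder but cannot remove one. DoR suffers too. It is analysed in confirmed responders only, so such a participant enters the DoR analysis with almost no follow-up. Two programmers could also handle the case differently, because the SAP does not address it.

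**Working it through.** **1. The rules side by side**

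| Item | PFS and DoR (SAP Table 3, 5.4.4) | ORR (SAP 5.3, 8.1; Protocol Appendix 3) |
|---|---|---|
| Closes at progression | Yes | Yes |
| Closes at new therapy or procedure before progression | Yes, at the last adequate earlier assessment | Not stated |
| Limit on the confirming scan | Not applicable | At least 4 weeks; nothing else |

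**2. A route that meets every written condition**

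Take nominal visit days. A first PR is seen at C3D1, Day 57. New treatment starts 7 weeks later, before documented progression: Day 57 + 49 = Day 106, ahead of the next scheduled scan at C5D1, Day 113. The treatment is a reason to stop nirogacestat, and the EOT visit follows within 7 days of that decision. If the decision falls on Day 106, EOT is between Day 106 and Day 113.

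- Time since the last scan: 49 to 56 days. This exceeds 6 weeks (42 days), so an EOT scan is required.
- Time since the response criteria were first met: also 49 to 56 days. This exceeds 4 weeks (28 days), so the EOT scan can confirm.
- ORR: if the scan still meets PR, the participant is a confirmed responder.
- DoR: it starts at Day 57. The last adequate assessment before the new therapy is also Day 57, so DoR is censored at about zero.

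If the response is instead first seen at this EOT scan, confirmation needs a further scan at least 4 weeks later, which the schedule does not contain. Only with such an unscheduled scan would the DoR censoring date fall before the response date.

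**3. Size**

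Inputs: planned N = 43 (SAP 1.4); 53 enrolled (SAP 5.8 and 6), assuming all were treated and form the Full Analysis Set; target ORR 30%, prior beta(0.1, 0.9), reference rate 15% and promising threshold 0.85 (SAP 1.4). The number of affected responders is not given; one or two is assumed.

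The exact 95% CI has lower limit Beta⁻¹(0.025; x, N−x+1) and upper limit Beta⁻¹(0.975; x+1, N−x). At 13/43 this gives 17.2% to 46.1%, which reproduces SAP Table 2. The posterior is P(ORR > 15%) = 1 − F(0.15; 0.1+x, 0.9+N−x), with F the beta distribution function.

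Shift per participant: 1/43 = 2.3 points; 1/53 = 1.9 points.

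| N | Responders | ORR % | 95% CI | P(ORR > 15%) |
|---|---|---|---|---|
| 43 | 13 | 30.2 | 17.2–46.1 | 0.992 |
| 43 | 12 | 27.9 | 15.3–43.7 | 0.980 |
| 43 | 11 | 25.6 | 13.5–41.2 | 0.955 |
| 53 | 16 | 30.2 | 18.3–44.3 | 0.997 |
| 53 | 15 | 28.3 | 16.8–42.3 | 0.991 |
| 53 | 14 | 26.4 | 15.3–40.3 | 0.980 |

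Near the 30% target, removing one or two responders leaves the posterior well above 0.85. It crosses 0.85 at a single step for each N: 10 to 9 responders of 43 (0.906 to 0.823), and 12 to 11 of 53 (0.915 to 0.846).

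**The case against.** The case for leaving the SAP alone is that other rules close nearly every route.

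- **Progression.** Best overall response already ends there. A reader might infer that ordinary next-line therapy after progression could add responders; the documents exclude that, because SAP 5.3 has to be read with SAP 8.1.
- **Eligibility and prohibited therapy.** Inclusion criterion 3 (Protocol 7.1) requires relapsed disease not amenable to surgery or radiation. Protocol 8.3.3.2 does not permit resection or other antineoplastic therapy on study, and limits palliative radiation to non-target lesions. Under the response table, such radiation could at most move a PR to a CR when the target lesions have already gone; it could not make a responder out of stable target lesions.
- **Scan schedule.** No tumor imaging is scheduled after EOT, and EOT comes soon after the decision to stop, which leaves a new drug little time to act. A reader might infer that new treatment can readily create a response from nothing; that needs an unscheduled confirming scan.
- **Coding.** A site might record resected target lesions as not evaluable rather than as gone.

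All of this stands as a limit on frequency. It does not settle how a post-therapy scan is analysed if one exists. The conduct rules are silent on that, and Table 3 contains a new-therapy rule despite the same prohibitions. SAP 4.10 keeps unscheduled assessments out of summary statistics unless otherwise indicated, but the EOT scan is scheduled. The check in SAP 5.8 that varies the responder count by 1 to 3 belongs to the interim evaluation, which SAP 6 says was not performed.

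**Conclusion.** The gap is real but narrow. It concerns participants who start new anticancer therapy or have a procedure before documented RECIST progression and are scanned afterwards. For them the plan as written can count a response whose confirmation, or rarely whose first appearance, came after that treatment. No planned analysis would reveal it.

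The bias is upward only: 1.9 points of ORR per participant if 53 are analysed, 2.3 if 43. The number of such participants is unknown and probably small.

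Two stronger readings are not supported. First, one might say that these participants have no valid DoR. In the main route DoR is a censored value of about zero; a censoring date before the response date arises only with the extra unscheduled scan. Second, one might say that a single participant can overturn the trial's conclusion. That is so only exactly at the threshold. No formal hypothesis test is planned, the primary analysis is an estimate with an exact interval, and equation (4) of SAP 5.8 is written for 43 participants, so its use at 53 is an extrapolation.

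The change is still worth making, because it concerns the primary endpoint and costs little.

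**What to change.** Add to SAP 5.3 and to the best overall response paragraph of SAP 8.1: *Only tumor assessments on or before the earlier of documented progression and the start of any new anticancer therapy or procedure, as defined for Table 3, are used to determine or confirm best overall response. A response not confirmed by then counts as a non-response.*

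Define new anticancer therapy or procedure once, for both ORR and Table 3, and state whether permitted palliative radiation to non-target lesions counts. A narrower definition for ORR, such as radiotherapy to target lesions only, would leave part of the mismatch in place.

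The cost is a short SAP amendment. Table 3 already needs the start dates, so no new data are required, and patient management does not change. The downside is that ORR may fall by a responder or two, including a participant whose shrinkage was truly due to nirogacestat but was not confirmed in time.
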